11.2 Methods of statistical analyses

The null hypothesis that the 18% historical complete response rate at month 6 will be tested against a one-sided alternative of 40% or higher complete response rate with Durvalumab at month 6 in BCG refractory CIS of bladder. We use a Simon's two-stage design (Simon, 1989) based on the optimal two-stage designs and admissible designs (Jung et al. 2004) for Phase II single arm clinical trials.

In the first stage of this study plan, 13 patients will be accrued. If there are 3 or fewer responses in these 13 patients, the study will be stopped. Otherwise, 21 additional patients will be accrued for a total of 34. The null hypothesis will be rejected if 9 or more responses are observed in 34 patients. In summary 34 is the total number of subjects required, 13 is the number of subjects accrued during stage 1, if 3 or fewer responses are observed during stage 1, the trial is stopped early for futility, and, if 9 or fewer responses are observed by the end of stage two, then no further investigation of the drug is warranted. This design yields a one-sided type I error rate of 0.047 and power of 80% when the true response rate is 40%.

The primary analysis will be performed for the (complete) response rate based on month 6 mapping biopsy. We will use an exact probability method such as Chi-square and binomial tests.

n	n ₁	r ₁	r ₂	Type 1 Error	Power	EN ₀	Probability of early stopping	Interval for w	Comment
34	13	3	9	0.0473	0.8031	17.1	0.8061	[0,0.1243]	Optimal

*EN*₀ is the expected sample size for the trial when response rate is p0

Interval for w is the set of values w such that the design minimizes $w * 2I + (1 - w) * EN0$

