Sample Size Determination: The null hypothesis is the 18% historical complete response rate at month 6 will be tested against a one-sided alternative of 40% or higher complete response rate with Durvalumab at month 6 in BCG refractory CIS of bladder. We use a Simon's two-stage design (Simon, 1989) based on the optimal two-stage designs and admissible designs (Jung et al. 2004) for Phase II single arm clinical trials. The required total number of subjects is 34. 13 is the number of subjects accrued during stage 1. If 3 or fewer responses are observed during stage 1, the trial is stopped early for futility. If 9 or fewer responses of total 34 patients are observed by the end of stage two, then no further investigation of the drug is warranted. This design yields a one-sided type I error rate of 0.047 and power of 80% when the true response rate is 40% based on Simon's optimal two-stage design.

SCHEDULE OF STUDY ASSESSMENTS**Schedule of study assessments: Screening and Treatment Period (<<12 months: maximum of 13 doses, last infusion week 50>>)**

Assessments to be performed at the times stipulated in the table and as clinically required in the management of the subject.	Screening	All assessments to be performed pre-infusion unless stated otherwise				
		Baseline	Every 4 weeks	Every 3 months of 12 months treatment phase	Every 4 months of the 12 months surveillance phase	End of Trial visit
Day	-28 to -1	1	Day 1 of the week			
Week	-4 to -1	0	4, 8, 12, 16, 20, 24, 28, 32, 36, 40, 44, 48, (± 3 days)	14, 26, 38, 52 (± 14 days)	68, 86 104, (±14 days)	105 (±7 days)
Written informed consent/assignment of subject identification number	X					
Demography and history of tobacco and alcohol use	X					
Previous treatments for CIS of bladder	X					
Formal verification of eligibility criteria	X					
Hepatitis B and C; HIV	X					
Urine hCG or serum βhCG ^b	X	As clinically indicated				
Durvalumab administration		X	X			
Clinic visit with history and physical examination ^c	X	X	X		X	X

Schedule of study assessments: Screening and Treatment Period (<<12 months: maximum of 13 doses, last infusion week 50>>)

Assessments to be performed at the times stipulated in the table and as clinically required in the management of the subject.	Screening	All assessments to be performed pre-infusion unless stated otherwise					
		Baseline	Every 4 weeks	Every 3 months of 12 months treatment phase	Every 4 months of the 12 months surveillance phase	End of Trial visit	

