1. INTRODUCTION

1.1 Disease Background

Bladder cancer is the fifth most common cancer in the United States. Approximately 74,690 new cases (56,390 men and 18,300 women) and 15,580 deaths (11,170 men and 4,410 women) from bladder cancer would occur in the United States in 2014. Nearly 75% of newly diagnosed bladder cancers are non-muscle invasive bladder cancer (NMIBC) or “superficial bladder cancer”. CIS is a flat high-grade noninvasive urothelial carcinoma (UC) that has a high propensity for invasion and metastasis. It may occur in isolation or with a synchronous UC. Other than bladder, it could also occur in urothelium lines upper tract, prostatic and penile urethral. The incidence of CIS of bladder is about 14-19% based on the published data with multiple bladder biopsies.

Intravesical BCG remains the most effective treatment for non-muscle invasive bladder cancer. Its efficacy is attributed to immune response induced by BCG, which tends to wane over time. BCG refractory bladder cancer is commonly defined as recurrence after 2 induction courses of BCG, or recurrence within 6 months of completing induction and maintenance phase of BCG. Unlike TURBT for Ta and T1 UC, CIS cannot be completely resected by biopsy. Standard therapy for BCG refractory CIS is radical cystectomy. For patients who are unsuitable for or refuse radical cystectomy, one approach would be enhancing the protective immunity induced by intravesical BCG by adding agents like interferon- α (Lam et al, 2003). Alternative approaches would be intravesical valrubicin or intravesical gemcitabine. Although intravesical valrubicin is the only FDA approved salvage agent, its complete response rate was only 18% at 3 months and 4% at year 2 in BCG refractory or intolerant CIS (Dinney et al, 2013). There is an unmet need to develop more effective therapy for BCG refractory CIS of bladder. Based on the report of the FDA and AUA joint workshop in 2013, an agent with an initial CR rate of 40-50% at month 6 and a durable response rate of at least 30% would be considered meaningful for BCG refractory CIS (Jarow et al, 2014).

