1.3 Research hypothesis

The null hypothesis that the 18% historical complete response rate at month 6 will be improved to 40% or higher with Durvalumab at month 6 in BCG refractory CIS of bladder. Such hypothesis is supported by the high percentage of PD-L1 IHC positivity in CIS of urothelial bladder cancer and enrichment of PD-L1 expression in the BCG-induced bladder granulomata after BCG failure (Inman et al, 2007). Vascular inflammation induced by bladder mapping biopsy would facilitate the deposition of immune complex containing durvalumab (Investigator brochure) at the biopsy sites.

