1.4 Rationale for conducting this study

There is an unmet need to develop more effective therapy for BCG refractory CIS of bladder. To facilitate drug development in this disease setting, FDA and AUA held a joint workshop in 2013. Based on the report from this workshop, an agent with an initial CR rate of 40-50% at month 6 and a durable response rate of at least 30% would be considered meaningful for BCG

refractory CIS. Response rate at month 6 is chosen as the primary endpoint. The historical 18% month 6 complete response rate will be tested against a one-sided alternative of durvalumab treated patients would show a complete response rate 40% or higher. Response rate at year 2 as well as safety assessments was chosen as secondary objectives.

Durvalumab will be given at 1500 mg Q4W (equivalent to 20 mg/kg Q4W) IV infusion for 12 months. Population PK analysis indicated only minor impact of body weight (WT) on PK of durvalumab (coefficient of ≤ 0.5). A fixed dosing approach is preferred due to ease of use and reduced dosing errors.

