3. STUDY DESIGN

3.1 Overview of study design

This is a multicenter, open-label, Phase 2 study of Durvalumab to evaluate its antitumor activity for BCG refractory urothelial carcinoma in situ (CIS) of the bladder. We use a Simon's two-stage design (Simon, 1989) based on the optimal two-stage designs and admissible designs (Jung et al. 2004) for Phase II single arm clinical trials. In the first stage of this study plan, 13 patients will be accrued. If there are 3 or fewer responses in these 13 patients, the study will be stopped. Otherwise, 21 additional patients will be accrued for a total of 34. Durvalumab will be given every 4 weeks at 1500 mg IV for total of 12 months/13 doses. Cystoscopy with mapping biopsy and TURBT (if indicated) will be performed at

Clinical Study Protocol

Investigational Drug Substance: MEDI4736 Durvalumab (Medi4736)

Study Number MCC 18788/MCC18788/ESR-15-11326

Edition Number 1.9.4

Date 10/08/2018

baseline, month 6, and 24. Urine cytology with UroVysion test will be performed at baseline, month 6, and 24. Patients will be off study if any of the biopsies documented muscle invasive (T2 or above) urothelial carcinoma. Patients will also be off study if their month 6, 12, 18 biopsies showed persistent (month 6) or recurrent CIS or invasive (T1 or above) urothelial carcinoma. Otherwise, patient will remain on study until after the month 24 biopsy.

Historical controls will be used to assess the efficacy of Durvalumab. For exploratory analysis on PD-L1 expression, PD-L1 IHC will be performed with the SP263 antibody developed by Ventana. IHC positivity (either on tumor cells and/or infiltrating immune cells) will be assessed on the available mapping biopsy and or TURBT samples at time points defined in SCHEDULE OF STUDY ASSESSMENT.

Data Monitoring Committee (DMC) at Moffitt Cancer Center will monitor this phase 2 study initiated by Moffitt's investigator.

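### The 18% null rate is labelled a historical month 6 rate without a source, and the stated type I error of 0.047 holds only if rejection needs at least 10 of 34 responses, not the 9 that one sentence in section 11.2 allows

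*Combined protocol and SAP*

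**What the plan says.** Four places define the null rate p0 as 18% and attach month 6 to it:

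- Synopsis, Sample Size Determination: "The null hypothesis is the 18% historical complete response rate at month 6 will be tested against a one-sided alternative".
- Section 1.3: "The null hypothesis that the 18% historical complete response rate at month 6 will be improved to 40% or higher with Durvalumab".
- Section 1.4: "The historical 18% month 6 complete response rate will be tested against a one-sided alternative".
- Section 11.2: "the 18% historical complete response rate at month 6 will be tested against a one-sided alternative of 40% or higher complete response rate".

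None of them gives a reference for the 18% or names the treatment it describes. The one cited 18% complete response rate is in section 1.1, for intravesical valrubicin: "its complete response rate was only 18% at 3 months and 4% at year 2 in BCG refractory or intolerant CIS". The month 6 figure that does have a source is the target taken from the workshop report, "an initial CR rate of 40-50% at month 6", which supports the alternative of 40% and not the null. Section 3.1 adds: "Historical controls will be used to assess the efficacy of Durvalumab".

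On the final decision, section 11.2 gives two rules. One sentence reads: "The null hypothesis will be rejected if 9 or more responses are observed in 34 patients". The summary that follows it, and the table (r2 = 9), treat 9 or fewer responses as a negative trial. The synopsis and section 11.3 also give the 9-or-fewer rule. The table prints type I error 0.0473, power 0.8031, expected sample size 17.1 and early stopping probability 0.8061.

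**The concern.** The trial has one arm, so p0 is the whole comparator. What a rejection means depends on what the 18% stands for. As worded, a positive trial would be reported as beating a historical month 6 rate, yet the documents contain no sourced historical rate at month 6. The matching number suggests that a 3-month figure may have been carried over to a month 6 endpoint. The cited valrubicin population, refractory or intolerant, is also wider than the refractory population studied here.

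The second matter is independent of where the 18% comes from. The stated error rate belongs to one final boundary and section 11.2 prints two. A trial that passes stage 1 and ends with exactly 9 responses would be positive under one sentence and negative under the next.

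**Working it through.** **Inputs.** Section 11.2: p0 = 0.18, p1 = 0.40, stage 1 of 13 patients with a stop at 3 or fewer responses, 21 further patients, 34 in total, r2 = 9.

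**Formula.** With the final test rejecting at c or more responses,

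P(reject | p) = sum over x = 4 to 13 of Bin(x; 13, p) × P(Bin(21, p) ≥ c − x).

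**Reproducing the table.** With r2 = 9 read as failure at 9 or fewer, c = 10:

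- Early stopping at 0.18: P(Bin(13, 0.18) ≤ 3) = 0.8061.
- Expected sample size: 13 + 21 × (1 − 0.8061) = 17.07, printed as 17.1.
- Type I error at 0.18: 0.0473.
- Power at 0.40: 0.8031.

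All four agree with the plan. A search over two-stage designs with one-sided error at most 0.05 and power at least 0.80 returns the same design as Simon's optimal one. The arithmetic is therefore right for a true month 6 rate of 18% with rejection at 10 or more.

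**The other sentence.** With c = 9, type I error at 0.18 is 0.0819 and power at 0.40 is 0.8217. The difference in error, 0.0819 − 0.0473 = 0.0346, is the chance under the null of passing stage 1 and finishing with exactly 9 responses. The printed 0.0473 and 0.8031 match c = 10 and not c = 9, so the plan's own figures show which sentence is the slip.

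**The time point.** The documents do not give the true month 6 rate under historical treatment. Every rate below other than 18% is an assumption.

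| Assumed month 6 rate | P(reject), 10 or more | P(reject), 9 or more |
|---|---|---|
| 10% | 0.0009 | 0.0026 |
| 12% | 0.0033 | 0.0086 |
| 14% | 0.0098 | 0.0217 |
| 16% | 0.0233 | 0.0452 |
| 18% | 0.0473 | 0.0819 |
| 20% | 0.0844 | 0.1326 |

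The only trend in the documents is downward, from 18% at 3 months to 4% at year 2. If the month 6 rate lies between those values, the 10-or-more rule has error at or below 0.0473. The 20% row is shown for range only; nothing in the documents points to a rate above 18%.

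**The case against.** The strongest reply is that no contradiction about the time point has been shown. Section 1.1 reports one agent at 3 months, while the four statements of the null name no agent. Both can be true if the 18% at month 6 comes from another source. That stands: what is established is a missing source and a mismatch of labels, not a relabelled figure.

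It can also be said that the harm is small. Type I error is by definition computed at the null, p0 may be chosen as a benchmark, and a null set too high works against the drug. That largely stands too. It does not excuse the wording, because all four places call the rate historical and none calls it a benchmark.

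A reader might point out that the smallest rejecting result, 10/34 = 29.4%, falls below the 40% target. That is ordinary for a two-stage design, whose final boundary normally lies between p0 and p1, and it is no evidence of a fault.

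Finally, the 0.0819 has nothing to do with the time point and should not be used to make that part look larger. Agreed: the two parts are kept apart here. The boundary conflict stands on its own and needs no inference.

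**Conclusion.** Two conclusions, of different strength.

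The final boundary in section 11.2 contradicts itself. Taken literally, the 9-or-more sentence raises one-sided type I error from 0.0473 to 0.0819, for a gain in power from 0.8031 to 0.8217. This rests only on the plan's own inputs, with the stage 1 stop followed and all 34 patients assessed.

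The 18% is called a historical month 6 rate in four places without a source, and the only sourced 18% is a 3-month rate. That one was taken from the other is an inference. If it was, and response wanes, the month 6 test is conservative, and the harm lies only in the wording of the null and of a positive conclusion.

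A reader might infer more: that a 3-month rate was certainly misused, that section 1.1 is wrong, or that the design is anti-conservative or wrongly sized. The documents support none of these. They do not show where p0 came from or which statement is in error, they give no reason to expect a month 6 rate above 18%, and the design reproduces exactly at p0 = 18%.

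**What to change.** (a) In section 11.2, change the rejection sentence from 9 or more to 10 or more responses in 34 patients, to match r2 = 9, the synopsis and section 11.3.

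(b) The sponsor confirms the source and time point of p0. Then:

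- If a month 6 source exists, cite it beside p0. Change section 1.1 only if the reference cited there itself gives 18% at month 6; otherwise that statement may be accurate and should stay.
- If p0 is confirmed as the 3-month valrubicin rate, describe it in the synopsis, 1.3, 1.4 and 11.2 as a fixed 18% benchmark drawn from a 3-month rate. Say why it suits a month 6 endpoint, for example that it is conservative if response wanes. Word a positive result as exceeding an 18% benchmark, not a historical month 6 rate.
- If no source can be confirmed, call it a fixed 18% benchmark and drop the word historical.

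Keep p0 = 18%, n = 34 and the stop at 3 or fewer of 13. The cost is one corrected number, one source check, and either a citation or rewording in four places; enrolment is untouched. The downside, where the label changes, is that the comparison with history is stated less directly.

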11.3 Determination of sample size

The required total number of subjects is 34. 13 is the number of subjects accrued during stage 1. If 3 or fewer responses are observed during stage 1, the trial is stopped early for futility. If 9 or fewer responses of total 34 patients are observed by the end of stage two, then no further investigation of the drug is warranted. This design yields a one-sided type I error rate of 0.047 and power of 80% when the true response rate is 40% based on Simon's optimal two-stage design.

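### Section 11.2 counts 9 responses in 34 as both rejection of the null and failure; rejecting at 9 has a type I error of 0.082, not the stated 0.047

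*Combined protocol and SAP*

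**What the plan says.** The primary endpoint is the month 6 complete response rate. It is tested in a Simon two-stage design with a null rate of 18% and a one-sided alternative of 40% or higher. Stage 1 is stated consistently: "In the first stage of this study plan, 13 patients will be accrued" and "If there are 3 or fewer responses in these 13 patients, the study will be stopped". Otherwise 21 more patients are accrued, for a total of 34.

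Section 11.2 then states the final rule twice, in consecutive sentences:

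- "The null hypothesis will be rejected if 9 or more responses are observed in 34 patients"
- "if 9 or fewer responses are observed by the end of stage two, then no further investigation of the drug is warranted"

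Section 11.3 repeats the second form ("If 9 or fewer responses of total 34 patients are observed by the end of stage two"), and so does the sample size paragraph of the synopsis. The design table in section 11.2 lists n = 34, n1 = 13, r1 = 3 and r2 = 9, with type I error 0.0473, power 0.8031, expected sample size under the null 17.1 and probability of early stopping 0.8061. The synopsis, section 11.2 and section 11.3 each quote a one-sided type I error of 0.047 and power of 80%.

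**The concern.** The two sentences overlap at exactly 9 responses. Under the first, 9 of 34 rejects the null; under the second, 9 of 34 ends development. One design with one r2 has one boundary, so the type I error and power quoted in the same paragraph can belong to only one of these rules.

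This is the final go/no-go threshold of a single-arm, open-label trial judged against a historical rate. A cut-off fixed in advance is its main protection against a false claim of activity. If the trial ended on 9 of 34, the protocol could be cited for either conclusion after the data were known. If the rejection sentence were simply followed, the trial would run at an error rate higher than the one it reports.

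**Working it through.** **Inputs, all from section 11.2:** p0 = 0.18, p1 = 0.40, n1 = 13, stop if X1 ≤ 3, stage 2 size 21, n = 34.

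**Formula.** With c the smallest total that rejects the null,

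P(reject | p) = Σ (x = 4 to 13) P(X1 = x) × P(X2 ≥ c − x), where X1 ~ Bin(13, p) and X2 ~ Bin(21, p).

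**Step 1: reproduce the plan's figures.** r2 = 9 in the table is the largest total that does not reject, so c = 10.

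- Early stopping under the null: P(X1 ≤ 3 | 0.18) = 0.8061. The table says 0.8061.
- Expected sample size under the null: 13 + (1 − 0.8061) × 21 = 17.07. The table says 17.1.
- Type I error and power: see Step 2. They come to 0.0473 and 0.8031, as in the table.

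A search over two-stage designs with type I error at most 0.05 and power at least 0.80 also returned this design (13/34, r1 = 3, r2 = 9) as the one with the smallest expected sample size under the null. That agrees with its label in the table as optimal.

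**Step 2: compare the two cut-offs at p = 0.18.**

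| Stage 1 responses x | P(X1 = x) | P(X2 ≥ 10 − x) | Product, c = 10 | P(X2 ≥ 9 − x) | Product, c = 9 |
|---|---|---|---|---|---|
| 4 | 0.12581 | 0.16247 | 0.02044 | 0.32314 | 0.04065 |
| 5 | 0.04971 | 0.32314 | 0.01606 | 0.53841 | 0.02676 |
| 6 | 0.01455 | 0.53841 | 0.00783 | 0.75634 | 0.01100 |
| 7 | 0.00319 | 0.75634 | 0.00242 | 0.91310 | 0.00292 |
| 8 | 0.00053 | 0.91310 | 0.00048 | 0.98451 | 0.00052 |
| 9 to 13 | 0.00007 | – | 0.00007 | – | 0.00007 |
| **Sum (unrounded terms)** | | | **0.0473** | | **0.0819** |

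The same sum at p = 0.40 gives the power:

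| Final rule | Type I error (p = 0.18) | Power (p = 0.40) |
|---|---|---|
| Reject at 9 or more | 0.0819 | 0.8217 |
| Reject at 10 or more | 0.0473 | 0.8031 |
| Reject at 11 or more | 0.0236 | 0.7644 |

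Only the middle row matches the plan. The ratio of the error rates is 0.0819 / 0.0473 = 1.73.

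**Step 3: could another reading give 0.047 with a cut-off of 9?** Ignoring the stage 1 stop raises the error: 0.1444 for 9 or more of 34, and 0.0716 for 10 or more. Neither is 0.047.

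**Step 4: how often would the conflict matter?** It matters only if the trial passes stage 1 and ends on exactly 9 responses. That probability is the difference between the two rules:

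| True response rate | P(pass stage 1 and total = 9) |
|---|---|
| 0.18 | 0.0819 − 0.0473 = 0.035 |
| 0.25 | 0.3100 − 0.2385 = 0.072 |
| 0.30 | 0.5146 − 0.4488 = 0.066 |
| 0.40 | 0.8217 − 0.8031 = 0.019 |

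Of the four rates shown, the two intermediate ones carry the highest probability.

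**The case against.** The strongest reply is that the plan's arithmetic is right and its intention is easy to recover. The table reproduces in full. Failure at 9 or fewer appears in the synopsis, in the summary sentence of section 11.2, in the table as r2 = 9 and in section 11.3, whereas rejection at 9 or more appears once. The 0.047 figure directly follows the correct rule each time. A statistician working from the table would use 10, and the rules disagree at only one outcome. The synopsis and section 11.2.2 also call the efficacy analysis descriptive, and the stage 1 threshold is a second binding rule that is stated without conflict.

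Most of this stands. The fault is an inconsistent sentence, not a miscalculated design; 0.082 is what follows from obeying that sentence. The final cut-off is also not the trial's only decision threshold. But the odd sentence is the only one that says when the null hypothesis is rejected, and it sits in the statistical methods section, where an analyst would look. No text says which sentence prevails. Calling the analysis descriptive does not help while section 11.2 states a null hypothesis, a rejection rule and a type I error.

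One could also argue that rejecting the null and warranting further study are separate decisions, so that 9 of 34 might do the first and not the second. That fails, because the plan presents one design with one r2 and attaches a single error rate and power to it.

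**Conclusion.** The concern holds. Section 11.2 contradicts itself at exactly 9 of 34. Its rejection sentence, taken as written, has a one-sided type I error of 0.082 against the stated 0.047, with power of 0.822 against 0.803. The stated figures are correct for rejection at 10 or more. The calculation assumes independent binomial responses, the plan's rates of 18% and 40%, exactly 13 and 34 evaluable patients, and a stage 1 stop that is always obeyed. These assumptions also reproduce the plan's own table. The design itself is sound, and the practical exposure is the single outcome of 9 responses. Because that outcome decides the primary conclusion, the sentence needs correcting before the final analysis.

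**What to change.** In section 11.2, change the rejection sentence so that the null hypothesis is rejected if 10 or more responses are observed in 34 patients. This matches r2 = 9 in the table, the next sentence, the synopsis and section 11.3, and it makes the stated 0.047 and 80% correct for every statement of the rule. No other text needs to change for consistency on this point.

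The cost is one number in one sentence, made through the protocol's usual amendment process. Sample size, interim rule, data collection and conduct stay as they are. The correction should be dated before the final response count is known, so that it cannot be read as a choice made in light of the result.

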11.2.2 Efficacy Analyses

Descriptive statistics will be applied to Efficacy analyses/pathological response rates at month 6 and 24.

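### Section 11.2 names single-stage tests for the primary analysis that do not match its own two-stage rule, and does not say which criterion decides

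*Combined protocol and SAP*

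**What the plan says.** Section 11.2 frames the primary question as a one-sided test: "18% historical complete response rate at month 6 will be tested against a one-sided alternative of 40% or higher complete response rate with Durvalumab". The decision rule is a two-stage count. At stage 1, "If there are 3 or fewer responses in these 13 patients, the study will be stopped". If that bound is passed, "Otherwise, 21 additional patients will be accrued for a total of 34". The table in the same section gives type I error 0.0473, power 0.8031, expected sample size under the null 17.1 and probability of early stopping 0.8061.

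The final bound appears twice, in incompatible forms: "The null hypothesis will be rejected if 9 or more responses are observed in 34 patients", and shortly afterwards "if 9 or fewer responses are observed by the end of stage two, then no further investigation of the drug is warranted". Nine responses out of 34 reject the null under the first and fail under the second. The synopsis and section 11.3 carry only the second form.

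On the method for the month 6 response rate, section 11.2 says: "We will use an exact probability method such as Chi-square and binomial tests". No significance level, sidedness, continuity correction or allowance for the stage 1 stop is attached to these tests. Section 11.2.2 describes the efficacy analysis differently: "Descriptive statistics will be applied to Efficacy analyses/pathological response rates at month 6 and 24". The synopsis also calls the primary and secondary analyses descriptive. No estimator is named and no confidence interval for the response rate is planned; the term appears only in the abbreviation list.

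**The concern.** The quoted error rates belong to a procedure that can stop at 3/13. An ordinary binomial or chi-square test on the final 34 patients treats them as a single fixed sample, so its p-value is not the one the design implies. If such a test is run and reported as the primary analysis, its verdict can differ from the verdict of the count rule.

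The plan does not say which prevails, and the choice of test is left open. For an outcome on the boundary, the result of the primary endpoint would then depend on a choice made after the data are known. If the binomial test were taken as the criterion, the trial would also lose the 80% power on which its size was justified.

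**Working it through.** **Inputs (section 11.2).** p0 = 0.18, p1 = 0.40, n1 = 13, stage 1 stop at 3 or fewer, n = 34, so n2 = 21.

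**1. Reproduce the plan's figures.** For a final cut-off r,

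P(reject | p) = Σ over x = 4,…,13 of Bin(x; 13, p) × P(Bin(21, p) ≥ r − x).

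| Final rule | Type I error (p = 0.18) | Power (p = 0.40) |
|---|---|---|
| 9 or more | 0.0819 | 0.8217 |
| 10 or more | 0.0473 | 0.8031 |
| 11 or more | 0.0236 | 0.7644 |

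The probability of early stopping is P(Bin(13, 0.18) ≤ 3) = 0.8061. The expected sample size is 13 + (1 − 0.8061) × 21 = 17.07. All four tabulated figures are reproduced with rejection at 10 or more. Rejection at 9 or more does not reproduce the type I error or the power.

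**2. Apply each criterion at 10/34, stage 1 passed.**

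- Two-stage exact p-value: P(stage 1 passed and total ≥ 10 | 0.18) = 0.0473. The design rejects.
- Single-stage exact binomial: P(Bin(34, 0.18) ≥ 10) = 0.0716. This is above both 0.05 and 0.0473.
- One-sample chi-square, as its signed root: the standard error is √(0.18 × 0.82 / 34) = 0.0659.
  - Uncorrected: z = (0.2941 − 0.18)/0.0659 = 1.732; p = 0.042 one-sided, 0.083 two-sided.
  - Continuity-corrected: z = (9.5/34 − 0.18)/0.0659 = 1.509; p = 0.066 one-sided, 0.131 two-sided.

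So the binomial disagrees with the design, and the chi-square can fall either side of 5% depending on options the plan does not set. The chi-square uses a normal approximation and is not an exact method.

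**3. If a one-sided 5% binomial test governed.** The plan states no level for the named test, so 5% is an assumption; 0.0473 gives the same cut-off. At 11/34 the binomial p is 0.0316, so 11 responses would be needed. From the table, type I error becomes 0.0236 and power 0.764. The loss of power is 0.8031 − 0.7644 = 0.0387.

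**4. How often it matters.** With the design cut-off at 10, the one-sided binomial disagrees only at 10/34. The probability of passing stage 1 and ending on exactly 10 is 0.024 at a true rate of 18%, 0.088 at 30% and 0.039 at 40%. If the sentence rejecting at 9 were followed, 9/34 would also conflict (binomial p = 0.144).

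**5. Interval and estimate at 10/34.** The two-stage 90% interval takes its lower limit where P(stage 1 passed and total ≥ 10 | p) = 0.05, and its upper limit where P(stage 1 passed and total ≥ 11 | p) = 0.95.

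| | Two-stage | Standard exact (Clopper-Pearson) |
|---|---|---|
| 90% interval | 18.2% to 50.3% | 16.9% to 44.8% |
| 95% interval | 16.2% to 54.2% | 15.1% to 47.5% |

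The two-stage 90% interval excludes 18%, in agreement with the decision; the standard one does not. Both 95% intervals contain 18%, so 90% is the level that mirrors a one-sided 5% rule.

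The raw rate is 10/34 = 29.4%. The median-unbiased estimate is 31.2% and the uniformly minimum-variance unbiased estimate (UMVUE) is 36.2%. Over both stages the raw rate is biased by −2.0 percentage points at a true rate of 18%, −3.1 at 30% and −2.1 at 40%.

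**The case against.** The strongest reply is that the count rule plainly decides. Section 11.2 ties rejection of the null to a number of responses, not to a p-value, and the stage 1 stop is repeated in the synopsis and in sections 3.1, 3.3, 11.2.3 (interim analyses) and 11.3. On that reading the sentence on tests is loose description. This is the natural reading, and it rules out one inference a reader might draw: that the plan ignores its two-stage design. It does not. But the sentence is the only one that says how the primary response rate will be analysed, and nothing subordinates it to the bound, so the ambiguity remains.

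A reader might also infer that the named tests fail at 10/34. That is true of the binomial only. The uncorrected one-sided chi-square gives 0.042 and, at 5%, has the same cut-off of 10 as the design, because 9/34 gives 0.099.

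The reach is small. The binomial conflict is limited to one outcome, and the binomial errs on the conservative side. Both points stand, and they limit the seriousness of the defect without removing it.

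Finally, the choice of estimator is a trade-off. The UMVUE removes bias averaged over both stages but moves 10/34 well above the raw rate, and the median-unbiased estimate gives a different value. The documents do not favour one, so a design-adjusted estimate belongs beside the raw rate, not in place of it.

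**Conclusion.** The point holds as a mismatch within section 11.2. The section names single-stage tests, one of them not exact, beside a two-stage rule whose error rates those tests do not share, and it does not say which governs. At 10/34 the design's p-value is 0.0473 and the binomial's is 0.0716. If the binomial governed at an assumed one-sided 5%, power would be 0.764 instead of the stated 80%.

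The same section's sentence rejecting at 9 must be settled as part of this, because it implies a type I error of 0.082 against the stated 0.0473.

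It is tempting to go further and say that the planned estimate and confidence interval are wrong. The documents do not support that: they plan no interval and name no estimator. What can be said is that none consistent with the design is specified, and that a standard exact 90% interval, if used by default, would contradict the decision at 10/34.

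The figures assume the full 13 and 34 patients are analysed as designed. The arithmetic is certain; the practical reach is modest. This should be changed, but it does not undermine the design itself.

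**What to change.** In section 11.2:

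- State that the Simon bound is the decision rule for the primary endpoint: the null is rejected if stage 1 is passed and 10 or more of 34 patients respond.
- Correct the sentence that rejects at 9 or more, so that it agrees with the other statement of the bound and with the tabulated error rates.
- Replace the sentence naming chi-square and binomial tests with a two-stage exact p-value and a 90% confidence interval that accounts for the stage 1 stop, naming the ordering used (stage-wise in the figures above).
- Report the raw response rate, with one pre-specified design-adjusted estimate (UMVUE or median-unbiased) as a supplement.

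In section 11.2.2 and the synopsis, qualify the descriptive wording so that it does not cover the primary decision at month 6.

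The cost is a few sentences and a few lines of analysis code. Sample size, visits and patient procedures do not change.
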